### Numeric Results for a One-Sample Poisson Rate Test

Null Hypothesis:  $\lambda_1 \geq \lambda_0$  Alternative Hypothesis:  $\lambda_1 < \lambda_0$

Power	n	Target	Actual	$\lambda_0$	$\lambda_1$	Diff	Effect	Beta
		Alpha	Alpha			$(\lambda_1 - \lambda_0)$	Size	
0.9052	36	0.0250	0.0224	1.00	0.52	-0.48	0.6656	0.0948
0.9048	42	0.0250	0.0221	1.00	0.55	-0.45	0.6068	0.0952
0.9012	55	0.0250	0.0213	1.00	0.60	-0.40	0.5164	0.0988
0.9030	73	0.0250	0.0232	1.00	0.65	-0.35	0.4341	0.0970
0.9034	102	0.0250	0.0238	1.00	0.70	-0.30	0.3586	0.0966
0.9016	149	0.0250	0.0247	1.00	0.75	-0.25	0.2887	0.0984

#### Report Definitions

Power is the probability of rejecting a false null hypothesis. It should be close to one.

n is the size of the sample drawn from the population. To conserve resources, it should be small.

Alpha is the probability of rejecting a true null hypothesis. It should be small.

$\lambda_0$  is the value of the population mean rate under the null hypothesis.

$\lambda_1$  is the value of the population mean rate under the alternative hypothesis.

Diff is the value of  $\lambda_1 - \lambda_0$ , the difference being tested.

Effect Size is the value of  $(\lambda_1 - \lambda_0) / \sqrt{\lambda_1}$ .

Beta is the probability of accepting a false null hypothesis. It should be small.

### 12.3. Safety Sample Size Determinations

The freedom from device-related complications observed in CHAMPION over 2 years was 98.6%. For the two-year primary safety endpoint of freedom from device-related complications, using an exact one-sided test for one-sample binomial proportions with alpha of 0.025 (equivalent to 2-sided test at alpha of 0.05) (see table below), a sample size of 137 subjects will provide greater than 90% power to detect a difference as small as 10% from the null proportion rate of 0.80 (i.e., objective performance criterion of 80%). For sensor failures at 2 years, a sample size of 292 subjects provides greater than 90% power to detect a difference as small as 5.0% from the null proportion rate of 0.90 (i.e., objective performance criterion of 90%)(see table below).

To account for early withdrawal, and to allow additional countries to enroll sufficient number of subjects each, 800 subjects will be enrolled.

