## Clinical Investigation Plan

### **12. STATISTICAL ANALYSIS**

The data will be summarized using univariate statistics (e.g., N, mean, standard deviation, median, minimum and maximum) or frequency (e.g., N, %) as appropriate for continuous or categorical variables, respectively.

The primary time point for safety analyses is 24 months post enrollment. Enrollment is defined as having a successful Sensor implant. The primary time point for effectiveness analyses is 12 months post enrollment.

Unless otherwise specified, all statistical tests will be 2-sided with a significance level of 0.05.

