#### **12.1. Populations for Analysis**

**Safety Population:** The Safety Population consists of all subjects who received a Sensor implant or underwent the implant procedure but were never implanted, regardless of study completion status. All safety analyses will be performed on the Safety population.

Subjects who are found not to have an appropriately sized pulmonary artery branch and did not receive the Sensor implant will be considered ineligible for the study. However, these subjects will be followed for 30 days for safety and all safety related data for these subjects will be provided.

**Effectiveness Population:** The effectiveness population consists of all subjects who received a Sensor implant regardless of study completion status. All effectiveness analyses will be performed on the effectiveness population.

**Pooled Safety Population:** The Pooled Safety Population will consist of the Safety Population from this study and the Safety Population from other similar study(ies) (demonstrated to be poolable with this study) that have been combined to form a larger safety analysis population to permit more robust analyses.

**Pooled Effectiveness Population:** The Pooled Effectiveness Population will consist of the Effectiveness Population from this study and the Effectiveness Population from other similar study(ies) (demonstrated to be poolable with this study) that have been combined to form a larger effectiveness analysis population to permit more robust analyses.

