#### **12.7.1. Primary Safety Endpoints**

The primary safety analysis will be based on the following objective performance criteria: the lower limit of the one-sided 97.5% confidence interval on the freedom from device / system-related complication rate at 24 months is greater than 80% and b) the lower limit of the one-sided 97.5% confidence interval on the freedom from pressure sensor failure rate at 24 months is greater than 90%. The study will be judged to have provided positive safety results if both tests of the primary safety analysis endpoints are statistically significant (i.e.,  $p < 0.025$ ).

Mathematically stated, the primary safety hypotheses are:

$$H_0: P_{(\text{Freedom from device / system-related complications at 24 months})} \leq 80\%$$

$$H_a: P_{(\text{Freedom from device / system-related complications at 24 months})} > 80\%$$

$$a) \quad H_0: P_{(\text{Freedom from pressure sensor failure at 24 months})} \leq 90\%$$

$$H_a: P_{(\text{Freedom from pressure sensor failure at 24 months})} > 90\%$$

Plotting and analysis of safety endpoints will also be displayed using Kaplan-Meier methods.

*This confidential document is the property of Abbott and shall not be reproduced, distributed, disclosed or used without the express written consent of Abbott*

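### Section 12.7.1 does not name the analysis that decides the two 24-month safety criteria or say how event-free exits count, and section 12.1 leaves never-implanted subjects in the sensor-failure population

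*Combined protocol and SAP*

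**What the plan says.** Section 12.7.1 calls the safety result positive only if both criteria are met. The sensor criterion is that "the lower limit of the one-sided 97.5% confidence interval on the freedom from pressure sensor failure rate at 24 months is greater than 90" per cent; the complication criterion has the same form with 80%. The section gives no method for the interval and then adds: "Plotting and analysis of safety endpoints will also be displayed using Kaplan-Meier methods". The only test named for these endpoints is in section 12.3, which sizes them "using an exact one-sided test for one-sample binomial proportions with alpha of 0.025". The synopsis describes both as proportions of subjects.

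The plan expects incomplete follow-up: "To account for early withdrawal, and to allow additional countries to enroll sufficient number of subjects each, 800 subjects will be enrolled". Section 11.5 ends safety reporting at withdrawal or death. Section 12.4 rules out imputation unless later text provides for it, and no later text does so for the safety endpoints. Section 9.1.1 makes a death a complication only when the adverse event is at least possibly system-related.

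Section 12.1 defines the Safety Population as "all subjects who received a Sensor implant or underwent the implant procedure but were never implanted, regardless of study completion status" and uses it for all safety analyses. It also says that subjects without a suitable artery who "did not receive the Sensor implant will be considered ineligible for the study", and that "these subjects will be followed for 30 days for safety". The 24-month clock runs from enrollment, and "Enrollment is defined as having a successful Sensor implant".

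**The concern.** A binomial proportion needs a known 24-month status for everyone in its denominator. A subject who withdraws, is lost or dies of an unrelated cause without an event has none. That subject could be counted as event-free, counted as a failure, dropped or censored, and the plan does not choose. In an open-label study the choice would then be made with the data in view.

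The population problem is separate. Sensor failure as defined in section 9.1.2 presupposes an implanted sensor. A never-implanted subject kept in that denominator has no 24-month time point and cannot fail. Counted as event-free, such subjects can only raise apparent sensor freedom.

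**Working it through.** **The plan's own figures.** The exact binomial rule rejects at the smallest count r with P(Bin(n, P0) ≥ r) ≤ 0.025.
- Complications, n = 137, P0 = 0.80: r = 119, alpha 0.0245, power 0.910 at 0.90.
- Sensor failure, n = 292, P0 = 0.90: r = 273, alpha 0.0242, power 0.902 at 0.95.

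Both match section 12.3, as do all 14 rows of the two tables. At n = 800 the rule needs 663 event-free for complications (alpha 0.0218) and 737 for sensor failure (alpha 0.0231).

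**Assumptions.** The documents give no exit, death or failed-implant rates. I take 800 implanted subjects, constant hazards, and exits independent of failure. Let p be true 24-month freedom, e the exit share, and 24 months one unit of time:
- λ = −ln p and μ = −ln(1 − e)
- share with an observed failure: f = λ/(λ+μ) × [1 − exp(−(λ+μ))]
- share completing event-free: c = p(1 − e)

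**Readings for the sensor criterion.**
- Exits event-free: X ~ Bin(800, 1 − f), pass if X ≥ 737.
- Unknown status dropped, observed failures kept: n ~ Bin(800, f + c), X ~ Bin(n, c/(f + c)), with the exact critical count for each n.
- Exits as failures: X ~ Bin(800, c), pass if X ≥ 737.
- Kaplan-Meier with a log-log 97.5% lower limit, exits censored: simulated, at least 10,000 trials per setting.

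**Worked case, p = 0.93, e = 0.20.** λ = 0.0726, μ = 0.2231, f = 0.0628, c = 0.744. The binomial parameters are 0.9372 (event-free), 0.744/0.8068 = 0.9221 (dropped) and 0.744 (failures).

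Chance of passing the sensor criterion:

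| True freedom, exits | Exits as failures | Unknown status dropped | Kaplan-Meier | Exits event-free |
|---|---|---|---|---|
| 90%, 20% | about 0% | 0.2% | about 2% | 15% |
| 93%, 20% | about 0% | 46% | about 80% | 97% |
| 93%, 30% | about 0% | 25% | 76% | 99% |
| 95%, 20% | about 0% | 98.7% | about 100% | about 100% |
| 95%, 30% | about 0% | 94% | about 100% | about 100% |

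A fifth reading drops every exit, even after an observed failure. It gives about 2%, 75%, 68%, 99.8% and 99% for the same rows, but it discards observed primary events and is hardly plausible.

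Dropping unknown status is conservative because it removes only event-free exits: at true 90% and 20% exits the expected rate is 0.720/(0.0898 + 0.720) = 88.9%.

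**Exits as failures.** With 64 exits (8.0%), 800 − 64 = 736 < 737, so the sensor criterion fails with no sensor failure at all. With 138 exits (17.3%), 800 − 138 = 662 < 663, so the complication criterion fails with no complication.

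**Reported rate.** At 98.6% complication-free and 20% exits, the expected reported rate is 98.7% (event-free), 98.4% (unknown status dropped) or 78.9% (as failures).

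**Never-implanted subjects.** Add k automatic successes to 800 implanted, with true freedom 90%:

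| k | Critical count / n | Needed among 800 implanted | False-pass rate |
|---|---|---|---|
| 0 | 737/800 | 737 | 2.3% |
| 8 | 745/808 | 737 | 2.3% |
| 16 | 752/816 | 736 | 3.1% |
| 24 | 759/824 | 735 | 4.1% |
| 40 | 774/840 | 734 | 5.3% |

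**The case against.** - **The criteria do not plainly rest on a binomial.** A reader might infer that they do, because section 12.3 is explicit. The decision rule in 12.7.1 fits either a binomial or a Kaplan-Meier limit, and the section promises a Kaplan-Meier analysis. This stands: the defect is that the deciding analysis is unnamed, not that a wrong one is prescribed.
- **Section 12.4 narrows the readings.** Not imputing argues against counting exits as event-free or as failures. Dropping unknown status and Kaplan-Meier both keep the false-pass rate below 2.5%, so under them the risk is lost power near the criterion rather than a false safety claim. This also stands, but 12.4 does not choose between them. Section 12.1 pulls the other way: keeping subjects whatever their completion status sits badly with dropping exits.
- **A true rate of 93% is my choice.** The plan's sensor table starts at 95%, where the readings other than exits-as-failures nearly agree. This limits the practical effect and is part of the conclusion.
- **The never-implanted point is small and partly addressed.** Enrollment requires an implant, and small-artery subjects are called ineligible, so their place in the primary denominator is unclear. Others attempted but not implanted are clearly included, and nothing exempts the sensor endpoint from the Safety Population rule.

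**Conclusion.** The point holds as an unspecified deciding analysis plus a denominator that does not fit the sensor endpoint. It should be fixed, but it does not threaten the expected result. The safety verdict depends on the unstated rule when true sensor freedom lies close to 90%, or if exits are counted as failures. Well above a criterion, as with the cited 98.6% against 80%, only exits-as-failures changes the verdict, although the reported rate still moves.

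A reader might infer that the study is likely to pass wrongly, or that it is too small. The documents support neither. Inflation from exits arises only if they count as event-free, which section 12.4 argues against. The sample-size tables are correct, and 800 is far above 137 and 292. Inflation from never-implanted subjects is modest, absent at 8 such subjects, and calculated at a true rate of exactly 90%.

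All sizes rest on assumed exit and never-implanted shares, constant hazards and exits unrelated to failure.

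**What to change.** **Section 12.7.1.** Base both criteria on the 24-month Kaplan-Meier estimate with a one-sided 97.5% log-log lower limit. Censor withdrawals, losses and deaths not related to the device at last known status; a device-related death is already an event under section 9.1.1. Keep the exact binomial as a sensitivity analysis with its exit rule written down.

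**Sections 12.1 and 12.7.1.** Restrict the sensor-failure endpoint to implanted subjects. Keep never-implanted subjects in the complication analysis, censored at last follow-up, and say explicitly whether small-artery subjects are among them. Adjust the time origin in section 12 so that these subjects have a start time, for example the implant procedure.

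**Cost.** A protocol amendment submitted to the ethics committee (section 14.2). The binomial power tables become approximate, which is harmless at 800. Kaplan-Meier relies on exits being unrelated to failure: if 5%, 10% or 20% of true sensor failures were unexplained stops in transmission that got censored, it would pass 5.5%, 12.1% or 40.0% of the time at true 90% with 10% exits. A sensitivity analysis counting such stops as failures would address this. It and competing-risk curves for unrelated death are useful but optional.

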## Clinical Investigation Plan

### Tests for One Proportion - Freedom from Device-related Complications

Numeric Results for Testing One Proportion using the Exact Test

Alternative Hypothesis: One-Sided (H0: P ≤ P0 vs. H1: P > P0)

Power*	n	Proportion		Difference	Target Alpha	Actual Alpha*	Reject H0
		Given H0	Given H1				
0.91001	137	0.8000	0.9000	0.1000	0.0250	0.0245	119
0.90023	107	0.8000	0.9100	0.1100	0.0250	0.0233	94
0.90756	88	0.8000	0.9200	0.1200	0.0250	0.0238	78
0.92186	75	0.8000	0.9300	0.1300	0.0250	0.0243	67
0.92273	62	0.8000	0.9400	0.1400	0.0250	0.0238	56
0.90933	48	0.8000	0.9500	0.1500	0.0250	0.0248	44
0.91958	41	0.8000	0.9600	0.1600	0.0250	0.0244	38
0.91882	34	0.8000	0.9700	0.1700	0.0250	0.0226	32
0.90520	26	0.8000	0.9800	0.1800	0.0250	0.0227	25

\* Power and actual alpha were computed using binomial enumeration of all possible outcomes.

### Tests for One Proportion – Freedom from Sensor Failures

Numeric Results for Testing One Proportion using the Exact Test

Alternative Hypothesis: One-Sided (H0: P ≤ P0 vs. H1: P > P0)

Power*	n	Proportion		Difference	Target Alpha	Actual Alpha*	Reject H0
		Given H0	Given H1				
0.90193	292	0.9000	0.9500	0.0500	0.0250	0.0242	273
0.91154	193	0.9000	0.9600	0.0600	0.0250	0.0242	182
0.91132	127	0.9000	0.9700	0.0700	0.0250	0.0250	121
0.90879	85	0.9000	0.9800	0.0800	0.0250	0.0245	82
0.96665	70	0.9000	0.9900	0.0900	0.0250	0.0242	68

\* Power and actual alpha were computed using binomial enumeration of all possible outcomes.

#### Report Definitions

Power is the probability of rejecting the null hypothesis when it is false. It should be close to one.

n is the size of the sample drawn from the population. To conserve resources, it should be as small as possible.

P0 is the value of the population proportion under the null hypothesis.

P1 is the value of the population proportion under the alternative hypothesis.

P1-P0 is the difference to be detected by the study.

Alpha (significance level) is the probability of rejecting the null hypothesis when it is true. It should be small.

Target Alpha is the significance level that the study design is meant to achieve.

Actual Alpha is the significance level that is actually achieved by the design.

Reject H0 If... gives the critical value(s) for the test.

### **12.4. Missing Data**

Missing data will be tracked in the Electronic Data Capture system; queries will be generated and provided to the site. In addition, St. Jude Medical representative, or designee will routinely perform remote data check and on site monitoring per monitoring plan. Data queries will be addressed until resolution. Missing data that are not resolved will not be imputed unless specified below.

### **12.5. Subject Accountability and Baseline Information**

Descriptive summaries will be generated to describe the disposition of all enrolled subjects.

### **12.6. Demographic and Baseline Information**

Descriptive summaries will be generated for all relevant baseline variables. These variables include, but are not limited to, demographic data and conditions at the time of enrollment.

### **12.7. Safety Analyses**

The safety analyses will be performed using the Safety Population. The data will be summarized using univariate statistics (e.g., N, mean, standard deviation, median, minimum and maximum) or frequency (e.g., N, %) as appropriate.

#### **12.7.1. Primary Safety Endpoints**

The primary safety analysis will be based on the following objective performance criteria: the lower limit of the one-sided 97.5% confidence interval on the freedom from device / system-related complication rate at 24 months is greater than 80% and b) the lower limit of the one-sided 97.5% confidence interval on the freedom from pressure sensor failure rate at 24 months is greater than 90%. The study will be judged to have provided positive safety results if both tests of the primary safety analysis endpoints are statistically significant (i.e.,  $p < 0.025$ ).

Mathematically stated, the primary safety hypotheses are:

$$H_0: P_{(\text{Freedom from device / system-related complications at 24 months})} \leq 80\%$$

$$H_a: P_{(\text{Freedom from device / system-related complications at 24 months})} > 80\%$$

$$a) \quad H_0: P_{(\text{Freedom from pressure sensor failure at 24 months})} \leq 90\%$$

$$H_a: P_{(\text{Freedom from pressure sensor failure at 24 months})} > 90\%$$

Plotting and analysis of safety endpoints will also be displayed using Kaplan-Meier methods.

*This confidential document is the property of Abbott and shall not be reproduced, distributed, disclosed or used without the express written consent of Abbott*

## Clinical Investigation Plan

Safety will also be assessed throughout the study by the frequency of Adverse Events (AEs), Adverse Device Events (ADEs), Serious AEs (SAEs), Serious Adverse Device Event (SADEs), unanticipated serious adverse device effects (USADEs), and device / system-related complications by relationship to the device via Medical Dictionary for Regulatory Activities (MedDRA) preferred term. Physical examination, and subject survival data through 24 months will be tabulated across study period assessments.

### 12.8. Effectiveness Analyses

Effectiveness analyses will be conducted in the effectiveness population. The data will be summarized using univariate statistics (e.g., N, mean, standard deviation, median, minimum and maximum) or frequency (e.g., N, %) as appropriate.

#### 12.8.1. Primary Effectiveness Endpoint

The primary time point for analyses is 12 months post-enrollment. The primary effectiveness endpoint will compare the annualized HF hospitalization rate parameter,  $\gamma$ , at 1 year versus the HF hospitalization rate in the year prior to enrollment using a one-sample, one-sided Poisson rate test. If the one-sided, upper 97.5% confidence interval for the PMS rate parameter is less than the rate in the year prior to enrollment, then the primary effectiveness endpoint will be met.

Mathematically stated, the primary effectiveness hypothesis is:

$$H_0: \gamma_{(12 \text{ month HF Hospitalization Rate})} \geq \gamma_{(\text{HF hospitalization rate in year prior to enrollment})}$$

$$H_a: \gamma_{(12 \text{ month HF Hospitalization Rate})} < \gamma_{(\text{HF hospitalization rate in year prior to enrollment})}$$

where  $\gamma_{(12 \text{ month HF Hospitalization Rate})}$  = the HF hospitalization rate parameter at 1 year in the PMS and  $\gamma_{(\text{HF hospitalization rate in year prior to enrollment})}$  = the HF hospitalization rate in the year prior to enrollment.

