## Clinical Investigation Plan

### 2. PROTOCOL SYNOPSIS

Sponsor:	St. Jude Medical, Atlanta, GA
Protocol Title:	CardioMEMS HF System OUS Post Market Study
Document Control Number:	SJM-CIP-10147
Device:	The CardioMEMS™ HF System consists of a wireless, battery-less pressure sensor implanted into the pulmonary artery and an external electronics that powers and communicates with the sensor and transmits pulmonary artery pressure waveforms and measurements to a secure website for Investigator review and patient management.
Purpose:	The purpose of this Post Market Study (PMS) is to evaluate the use of the CardioMEMS™ HF System in patients with Class III Heart Failure in a real-world setting.
Objective:	The objective of this PMS is to confirm safety and effectiveness in a real-world setting.
Study Population:	
Adults with New York Heart Association (NYHA) Class III Heart Failure (HF) who have experienced a heart failure hospitalization within the past 12 months.
 
The patients will serve as their own historical controls for effectiveness (1 year prior to implantation).
 
All subjects who sign the informed consent form and satisfy the inclusion/exclusion criteria.
 
Ejection fraction data must be taken within the last 6 months or prior to implantation.

Study Design:	
This is a prospective, multi-center, open-label trial conducted in centers located outside of the United States (US).
 
All subjects who sign the informed consent form and satisfy the inclusion/exclusion criteria will be enrolled into the CardioMEMS™ HF System PMS and will be scheduled for follow-up visits at 1 month and every 6 months for 2 years.
 
Following sensor implant and hospital discharge, subjects will take PA pressure measurements on a daily basis, or as directed by the investigator. These measurements will be automatically transmitted to the secure patient database (Merlin.net website).

Timeline:	Study visits will be scheduled at Month 1, Month 6, and every 6 months thereafter for 2 years or until study termination.

*This confidential document is the property of Abbott and shall not be reproduced, distributed, disclosed or used without the express written consent of Abbott*

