#### **6.1. Inclusion Criteria**

1. Written informed consent obtained from subject
2.  $\geq 18$  years of age
3. Diagnosis of NYHA Class III Heart Failure
4. At least 1 HF hospitalization within 12 months of Baseline visit
5. Subjects with reduced LVEF heart failure should be receiving a beta blocker for 3 months and an ACE-I or ARB for one month unless in the investigator's opinion, the subject is intolerant to beta blockers, ACE-I or ARB.
6. Subjects with a BMI  $\leq 35$ . Subjects with BMI  $>35$  will require their chest circumference to be measured at the axillary level, if  $> 65$  inches the patient will not be eligible for the study.
7. Subjects with pulmonary artery branch diameter  $\geq 7\text{mm}$  - (implant target artery - assessed during the RHC)
8. Subjects willing and able to comply with the follow-up requirements of the study

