#### **8.1. Screening Visit**

During the screening visit, the following procedures/assessments will be performed to determine subject eligibility:

- Informed Consent prior to the conduct of any study-related procedures
- Physical examination including vital signs (temperature, heart rate, blood pressure), weight, height, BMI calculation (refer to Appendix D)
- Medical and surgical history including ejection fraction data must be taken within the last 3 months to enroll in the study. If ejection fraction data is older than six months, ejection fraction data is required to be obtained at screening visit or prior to implantation.
- Patient history of all heart failure hospitalizations in the 12 months previous to the baseline visit as documented with information provided by the patient's cardiologist, internist, or referring physicians and review of all source documents of any heart failure hospitalizations reported in the previous year.
- Demographics
- NYHA Functional Classification
- Calculation of GFR (requires creatinine - refer to Appendix E)
- Assessment of medications
- Assessment of enrollment eligibility (inclusion/exclusion criteria)
- Completion of Quality of Life Questionnaire EQ-5D-5L

Eligible subjects will be scheduled for the Implant procedure. Subjects on anticoagulation therapy (e.g. warfarin) may be instructed by the Investigator to discontinue use 1-2 days prior to pressure sensor placement. The investigator should consider utilizing enoxaparin (Lovenox) per the site's standard of care as bridge therapy to Sensor placement in subjects who were on anticoagulation therapy.

For subjects at risk for gastro-intestinal bleeding during the period in which dual antiplatelet therapy is given, the investigator should consider a proton pump inhibitor such as omeprazole (Prilosec). Subjects at risk include the elderly, those with a history of gastroduodenal ulcers, GERD, esophagitis, intestinal polyps or cancer. Subjects who smoke or who are using steroids or non-steroidal anti-inflammatory drugs may also be at risk.

*This confidential document is the property of Abbott and shall not be reproduced, distributed, disclosed or used without the express written consent of Abbott*

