#### **12.2. Sample Size Considerations**

##### **Effectiveness Sample Size Determination**

For the primary effectiveness endpoint of HF hospitalization rate during 1 year, 250 subjects will provide greater than 90% power to meet the efficacy goal, using a one-sample, one-sided Poisson rate test with alpha of 0.025.

The HF hospitalization (HFH) rate for Control and Treatment groups at 1 year in Part 1 of the CHAMPION trial were 0.75 and 0.52 (HFH/patient-year), respectively. For this trial, HF hospitalization rates at 1 year will be compared to the rate observed in the trial subjects 1 year prior to enrollment (i.e., 1.0 or greater). Using a one-sample, 1-sided Poisson rate test with alpha of 0.025 (equivalent to 2-sided test at alpha of 0.05) (see table below), at least 149 subjects will provide >90% power to show a difference between a Treatment rate as high as 0.75 (conservative estimate) and the subject's own

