## Clinical Investigation Plan

historical rate from the year prior estimated at a minimum of 1.0. To account for early withdrawal, and to allow additional countries to enroll sufficient number of subjects each, 800 subjects will be enrolled.

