##### 12.8.2.2. HF Hospitalization or Death

The annualized HF hospitalization or death rate parameter,  $\lambda$ , at 1 year will be compared to the HF hospitalization rate in the year prior to enrollment using a one-sample, one-sided Poisson confidence

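### The primary effectiveness test treats the subjects' own prior-year rate as a known constant, ignores pairing and assumes Poisson variance, so its one-sided alpha of 0.025 is not assured

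*Combined protocol and SAP*

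**What the plan says.** Section 12.8.1 compares the annualized HF hospitalization rate "at 1 year versus the HF hospitalization rate in the year prior to enrollment using a one-sample, one-sided Poisson rate test". The endpoint is met if the one-sided upper 97.5% limit of the on-study rate lies below the prior-year rate. The hypotheses in that section write both years with the same rate symbol, gamma.

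The comparator does not come from outside the trial. Section 12.2 says on-study rates "will be compared to the rate observed in the trial subjects 1 year prior to enrollment (i.e., 1.0 or greater"), and the synopsis says: "The patients will serve as their own historical controls for effectiveness (1 year prior to implantation"). Entry requires "At least 1 HF hospitalization within 12 months of Baseline visit" (section 6.1). Screening already collects "Patient history of all heart failure hospitalizations in the 12 months previous to the baseline visit" with source review (section 8.1).

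On sample size, section 12.2 states that "at least 149 subjects will provide >90% power to show a difference between a Treatment rate as high as 0.75" against the subject's own "historical rate from the year prior estimated at a minimum of 1.0". It also says 250 subjects give more than 90% power, and it plans 800. Section 12.8.2.2 repeats the rule for HF hospitalization or death, "using a one-sample, one-sided Poisson confidence" interval. Section 12.8.2.5 names no test for subgroups. No section gives a paired model, a robust variance, an overdispersion adjustment or a sensitivity analysis for this endpoint.

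**The concern.** A one-sample Poisson test is valid against a fixed external rate when events follow a Poisson law. Here the design is before-and-after in the same people, and the rule departs from it in three ways.

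- **Comparator error.** The prior-year rate is a sample mean, but no variance is attached to it. This raises the error rate.
- **Overdispersion.** Some patients are admitted repeatedly and others not at all, so the variance of the counts can exceed the mean. This also raises the error rate.
- **Pairing.** Positive correlation between a subject's two years reduces the variance of the difference. Ignoring it lowers the error rate.

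The three do not simply add, and the documents give no figures to net them out. At stake is the type I error of the primary effectiveness claim, and of the supplemental analysis that repeats the rule. The quoted power rests on the same fixed-comparator, pure-Poisson model.

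**Working it through.** **1. The plan's own figures.** Inputs from section 12.2: null rate 1.00, alternative 0.75, alpha 0.025 one-sided, n = 149. Reject if total events ≤ c, where c is the largest value with P(Poisson(149 × 1.00) ≤ c) ≤ 0.025.

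- c = 125, and actual alpha = 0.0247.
- Power = P(Poisson(149 × 0.75 = 111.75) ≤ 125) = 0.9016.

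Both match the table, and the other five rows reproduce too. The arithmetic is right; the question is whether the model fits the design.

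**2. Large-sample size of the rule.** Let phi and v0 be the on-study and prior-year variance/mean ratios and r the within-subject correlation. With equal true means, the variance the test should use, relative to the one it does use, is

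R = phi + v0 − 2r√(phi × v0), and size = Φ(−1.96/√R).

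| phi | v0 | r | R | size |
|---|---|---|---|---|
| 1 | 0 | – | 1.00 | 2.5% |
| 1 | 0.25 | 0.5 | 0.75 | 1.2% |
| 2 | 0.25 | 0 | 2.25 | 9.6% |
| 3 | 0.5 | 0.3 | 2.77 | 11.9% |

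These values of phi, v0 and r are assumptions. In the first row every subject has exactly one prior event and on-study counts are Poisson. The entry criterion makes each prior count at least 1, so a planning rate of exactly 1.0 implies that row. Any prior rate above 1.0, which section 12.2 allows, means prior counts vary, so v0 > 0. Sample size does not enter R, so enrolling more subjects does not remove the inflation.

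**3. Simulation with the entry criterion.** Gamma-Poisson counts share a subject-level frailty across both years, with at least one prior event. Untruncated rates of 0.5–1.5 are assumed, with n = 250 and 800. The follow-up mean is scaled to equal the truncated prior-year mean (factor 1.10–2.54), so the plan's null is true. Monte Carlo SE is 0.3 points or less.

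| Dispersion | One-sided error, plan's rule |
|---|---|
| 0 | 3.6–5.5% |
| 0.5 | 5.6–6.8% |
| 1 | 5.9–7.2% |
| 2 | 6.9–7.8% |
| 4 | 7.5–8.2% |

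A log rate ratio with subject-level robust variance gives 2.3–3.2% over the same settings.

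**4. Comparator truly constant at 1.0.** Only on-study overdispersion remains (variance = m + d·m²). Exact negative binomial sums at n = 800 give size 2.4%, 3.8%, 5.3%, 8.1% and 12.8% at d = 0, 0.25, 0.5, 1 and 2. At n = 250, size is 4.9% at d = 0.5 and 7.6% at d = 1.

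**5. Power.** With a known comparator of 1.0 and an on-study rate of 0.75:

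- n = 149: 90.2% falls to 88.2%, 86.5% and 83.8% at dispersion 0.25, 0.5 and 1.
- n = 250: 95.3%, 92.0% and 86.9% at dispersion 1, 2 and 4.

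If the comparator is estimated and both years are independent Poisson with no entry selection, the variance of the within-subject difference is 1.00 + 0.75 = 1.75. Then n for 90% power is (1.96 + 1.2816)² × 1.75 / 0.25² ≈ 295. Across the unselected scenarios tried (independent Poisson, and dispersion 0.5 to 1 with or without shared frailty), paired power was 58–85% at n = 250 and at least 97% at n = 800. In the model of step 3, the paired robust test at n = 800 had about 100% power for a rate ratio of 0.75 at dispersions 0, 1, 2 and 4.

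**The case against.** The strongest reply is that the benchmark is the cohort's realised prior-year rate, a performance goal, so comparator error does not count. Section 12.8.1 does not say this, and writing both years as the parameter gamma points the other way. Even on that reading the Poisson assumption remains, and step 4 shows it is enough to break the nominal alpha.

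Three further points stand in part:

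- **Pairing is not a source of inflation.** Taken alone, ignoring it makes the test conservative. Alpha is unassured in both directions, not uniformly inflated.
- **The effect on the decision at 800 is small.** In the step 3 model, the average observed rate ratio needed for success moves from about 0.94–0.965 under the plan to 0.93–0.95 under the paired test. Only a near-null result would change verdict.
- **Regression to the mean is the larger threat.** Selecting on a prior admission with no device effect and no rescaling of means, the plan's rule was met in 71–100% of simulated trials and the paired robust test in 51–100%.

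The last point limits what the correction achieves. It does not justify leaving the primary interval with an error rate that differs from the one stated.

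**Conclusion.** The concern holds. The claim is that the one-sided alpha of 0.025 is not assured, not that it is always exceeded. It is exact when every prior count is 1 and on-study counts are Poisson, and conservative when within-subject correlation is strong enough. In the selected gamma-Poisson model it is about 1.4 to 3.3 times nominal (3.6/2.5 to 8.2/2.5). All sizes depend on assumed dispersion, prior-year variance and correlation, because the documents give none. The defect in the rule itself can be read directly from the text. The power quoted for 149 and 250 subjects rests on a known comparator and no overdispersion. Power at 800 is not in doubt in the settings examined. This should be fixed, because the test decides the primary effectiveness endpoint and the remedy is cheap.

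**What to change.** Replace the test in 12.8.1 with wording such as:

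> HF hospitalizations in the year before and the year after implant will be analysed with two records per subject, a log person-time offset and a period effect, in a Poisson GEE with independence working correlation and robust variance clustered on subject. The endpoint is met if the one-sided 97.5% upper limit of the follow-up/prior rate ratio is below 1.

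A subject-level bootstrap of the rate ratio is an acceptable alternative.

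- **12.8.2.2:** use the same method, noting that deaths cannot occur in the prior-year record.
- **12.8.2.5:** name the method for subgroups.
- **12.2:** state that the power given for both n = 149 and n = 250 assumes a known comparator and no overdispersion.
- **Interpretation:** state that the change corrects the interval only. Regression to the mean remains, so a significant result would not by itself show a device effect.

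The cost is SAP wording and a standard model. Both years' hospitalizations are already collected, so no extra data or subjects are needed. Intervals would usually be somewhat wider, which the planned 800 can absorb.
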